Naltrexone and Bupropion Combination on Obese, Smoking
Patients With Schizophrenia

NCT02736474

2015.12.30.

Subjects: A total number of 60 subjects will be recruited for the study with 30 of them to complete the imaging assessment. The major inclusion criteria are: 1) diagnosis of schizophrenia; 2) age between 18 and 65 years; 3) on stable antipsychotic medication regimen for at least one month; 4) BMI \geq 28 kg/m² using the BMI criterion for obesity in the Chinese population; 5) smoking at least 10 cigarettes daily for a minimum of 1 year; 6) desire to lose weight and quit smoking. The exclusion criteria are: 1) binge eating or other eating disorders; 2) current use of weight loss medications; 3) current substance use (except nicotine or caffeine); 4) elevated hepatic transaminase levels (>2.5x normal range); 5) clinically significant TSH and/or T4 abnormalities; 6) history of seizure disorder; 7) history of unstable cardiac problems or other unstable medication conditions; 8) being pregnant or nursing (for women).

Screening visit: After written informed consent is obtained, a diagnosis of schizophrenia will be determined by the International Classification of Diseases 10th Revision (ICD-10) by a research psychiatrist. A medical history and physical examination will be obtained by a research psychiatrist to assess inclusionary and exclusionary criteria, including current medications, substance use and number of cigarettes smoked daily. A urine pregnancy test will

be performed for women of childbearing potential. In addition, a urine drug screen, and a 12-lead EKG will be performed.

Baseline visit: Eligible subjects will come to the clinic for the baseline assessment including: 1) height, weight and waist circumference; 2) Fasting blood samples for glucose, insulin, leptin, ghrelin, HbA1c, lipid profile, comprehensive metabolic profile, CBC, high sensitivity CRP, IL-6 and TNF- α ; 3) breath CO level; 4) smoking craving using the Visual Analogue Scale; 5) number of cigarettes smoked in the past week; 6) the Positive and Negative Syndrome Scale (PANSS), 7) the side effects questionnaire. On a separate day, subjects who participate in the imaging assessment will complete the brain MRI scans. Subjects will then receive the study drug (either combination medication or placebo). The randomization is based on a 1:1 ratio using permuted block randomization, stratified by imaging assessment participation. In addition, subjects will receive the first session lifestyle counseling.

Follow-up visits: Subjects will be followed at weeks 2, 4, then every 4 weeks to receive the study drug and the lifestyle counseling. Weight, breath CO, and possible side effects will be assessed during each visit. Waist circumference, scales, the clinical

symptoms assessment will be repeated every 4 weeks. Fasting blood samples for glucose, insulin, leptin, ghrelin, HbA1c, lipid profile, comprehensive metabolic profile, CBC, high sensitivity CRP, IL-6 and TNF- α will be repeated at weeks 12, 24. Those subjects who participate in the imaging assessment, will repeat the brain MRI scans at week 24.

Intervention: This is a randomized, double-blind, placebo-controlled study. Following screening and confirmation that inclusion and exclusion criteria are met, subjects will be treated with naltrexone sustained release 15mg once per day and bupropion sustained release 150mg once per day in the first two weeks. Then subjects take naltrexone 15mg twice per day and bupropion 150mg twice per day during the rest of the study. The dosing choice of NB is based on the efficacy and side effects of various dosing strategies reported in previous NB trials as well as the supply availability of both naltrexone and bupropion in China. Subjects will be maintained on the same antipsychotic at the same dose whenever possible during the study; however the subject's clinical well-being will determine antipsychotic dosing. Subjects will return to meet with an investigator every 2 weeks for the first 4 weeks, then every 4 weeks to review medical and psychiatric status. Compliance will be

assessed by pill counts at each meeting. Subjects also receive culturally sensitive lifestyle counseling during each visit.

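### Does the absence of a listed TSH/T4 test, and of a stated review of baseline liver results, leave two exclusion criteria unenforced?

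*Protocol*

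**What the plan says.** The exclusion list in the Subjects section of the Protocol includes "4) elevated hepatic transaminase levels (>2.5x normal range); 5) clinically significant TSH and/or T4 abnormalities". The liver criterion has a numerical limit; the thyroid criterion rests on clinical significance and has none.

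The Screening visit states how eligibility is assessed: "A medical history and physical examination will be obtained by a research psychiatrist to assess inclusionary and exclusionary criteria". It then adds a urine pregnancy test for women who could become pregnant, and "In addition, a urine drug screen, and a 12-lead EKG will be performed". It lists no blood draw.

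The Baseline visit begins "Eligible subjects will come to the clinic for the baseline assessment including", and its laboratory item reads "Fasting blood samples for glucose, insulin, leptin, ghrelin, HbA1c, lipid profile, comprehensive metabolic profile, CBC, high sensitivity CRP, IL-6", with TNF-α completing the list. After the assessments, and the MRI for the imaging subgroup, the text continues "Subjects will then receive the study drug (either combination medication or placebo". Under Follow-up visits the same panel "will be repeated at weeks 12, 24".

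The Intervention section opens its account of dosing with "Following screening and confirmation that inclusion and exclusion criteria are met, subjects will be treated with" and then gives the regimen.

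**The concern.** An exclusion worded in terms of TSH and T4 invites the question of where those hormones are measured, and no visit names them. Followed literally, the thyroid criterion would be settled by history and examination. These can reveal known or clinically apparent disease but do not produce a TSH or T4 value. The omission stands out because other exclusions have their test listed at screening: the drug screen for substance use and the urine test for pregnancy. The blood panel is also itemised down to individual cytokines.

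The liver criterion raises a question of sequence. The earliest listed source of a transaminase value is the baseline metabolic profile, which is drawn in people already called eligible. The Baseline visit then goes on to dispensing without mentioning that anyone reads the result.

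The stake is subject safety and adherence to the trial's own entry criteria. A person with an undetected abnormality could be randomised and treated although a stated exclusion applied.

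**Working it through.** No sample-size, power or event figure bears on this point, so the check sets each criterion against every listed assessment and then asks what the gap could do to the comparison.

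**Step 1: count what is listed.**

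| Visit | Listed procedures | TSH/T4 by name | Possible transaminase source |
|---|---|---|---|
| Screening | 6: diagnosis, history, examination, pregnancy test, drug screen, EKG | 0 | 0 |
| Baseline | 11 blood items: glucose, insulin, leptin, ghrelin, HbA1c, lipids, metabolic profile, CBC, hs-CRP, IL-6, TNF-α | 0 | 1 (metabolic profile) |
| Weeks 12 and 24 | same 11 items | 0 | 1 at each draw, after treatment starts |

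TSH/T4 is therefore named in 0 of 11 items at each of 3 draws, and 0 of the 6 screening procedures is a blood test. The 11 is a count of names, not of analytes, since three of the items (lipids, metabolic profile, CBC) are composites.

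**Step 2: state the assumption.** The documents do not define the metabolic profile. I assume that it contains transaminases and not thyroid hormones. If it also contained thyroid tests, the thyroid gap would vanish. If it lacked transaminases, the liver criterion would be in the same position as the thyroid one. Step 3 covers either case.

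**Step 3: read the visit lists with the Intervention section.** That section allows treatment only after the criteria have been confirmed, and it exempts none of them. A numerical liver limit cannot be confirmed without a value, and under the assumption the plan supplies one before the drug is given. The order of draw, result, confirmation and treatment is compatible with the text. Nothing says that drug is dispensed on the day of the blood draw. For the 30 imaging subjects the text places an MRI on a different day, ahead of dispensing. Read this way, being called eligible at baseline means having passed screening so far.

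For the thyroid criterion the same condition requires the investigator to reach a view. The history covers current medications, so known thyroid disease or thyroid treatment would come to light. The text neither provides for nor forbids an existing laboratory report or a routine assay. The case left uncovered is an abnormality that is unknown, not apparent on examination and still clinically significant.

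**Step 4: consequence for the comparison.** A missed thyroid or liver abnormality at entry exists before allocation. Randomisation is 1:1 in permuted blocks, so such subjects fall in either arm by chance. The SAP analyses by intention to treat, which keeps them in the arm to which they were allocated. If a liver result were read only after randomisation but before the first dose, the sample would still have been taken before treatment and the trial is double-blind, so exclusion on that result could not depend on the arm. None of these routes gives a systematic difference between groups.

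**The case for a change.** The strongest case for a change is that a requirement to confirm a criterion is hollow without a listed measurement to confirm it with. The confirmation sentence is tied to screening, which has no blood test. It names no laboratory result, and it governs treatment rather than randomisation. The plea that this is a condensed summary is weakened by the detail given elsewhere, with the full blood panel written out twice. No existing-records route, and no time window for one, is stated. The remedy would also be cheap: one assay on a sample already planned, and one sentence on reviewing results.

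Part of this stands. TSH and T4 appear nowhere outside the exclusion list, and a reader cannot tell from the text how a silent abnormality would be found. It is also true that the text does not spell out the liver review.

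It does not carry the point further. The protocol does not permit dosing a subject whose criteria are unconfirmed, so the missing words describe a step that is already required. The safety argument rests on inference: the documents give no reason for the thyroid exclusion, no frequency of undetected cases and no statement that results go unread. A low cost of amendment does not show that the plan is deficient.

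**Conclusion.** No change follows. The thyroid part is a genuine omission in wording: 0 of 11 named blood items, 0 of 3 draws and 0 of 6 screening procedures. It is one that investigators can fill sensibly, because they must confirm the criterion before treating anyone. The liver part is a drafting point, since a pre-treatment sample exists and the general confirmation covers it.

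The conclusion rests on three things: that the metabolic profile includes transaminases; that the confirmation sentence in the Intervention section applies to every exclusion, as it is worded; and that a short narrative protocol need not name each screening assay. The number of the 60 subjects who might be affected is not given and cannot be derived. The randomised comparison and its interpretation are not shown to be affected. Naming the thyroid test and the source of the liver result would make the text clearer, but the plan works without it.

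### Pregnancy is an exclusion, but the only pregnancy test listed is one urine test at screening; none is listed at first dose or during 24 weeks of dosing

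*Protocol*

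**What the plan says.** **Entry.** Protocol, Subjects, gives the eighth exclusion as "8) being pregnant or nursing (for women". The age range is 18 to 65, with no restriction to men or to women who cannot conceive.

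**Test.** Under Screening visit, a urine pregnancy test is to "be performed for women of childbearing potential". It is the only pregnancy test named in either document.

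**From screening to first dose.** Baseline is a separate clinic visit for people already found eligible. It lists seven items, none of them a pregnancy test. The sample of 60 has "30 of them to complete the imaging assessment", and for that group "On a separate day, subjects who participate in the imaging assessment will complete the brain MRI scans". The next sentence is "Subjects will then receive the study drug (either combination medication or placebo". No maximum time from screening to first dose is given. The Intervention paragraph has treatment follow confirmation of the entry criteria.

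**During treatment.** "Subjects will be followed at weeks 2, 4, then every 4 weeks to receive the study drug". The repeated assessments are set out: "Weight, breath CO, and possible side effects will be assessed during each visit"; waist, scales and symptoms every 4 weeks; the fasting blood panel "will be repeated at weeks 12, 24"; MRI again at week 24. An investigator also reviews medical and psychiatric status at the visits. No pregnancy test is among these items.

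**The concern.** Most of the exclusions concern history or a fairly stable condition. Pregnancy can begin at any time after a negative test. A single test at screening therefore shows that a woman was not detectably pregnant on that day. It does not show that she is not pregnant when drug is first handed over, and it cannot speak to the following 24 weeks.

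A site that follows the listed schedule has no instruction to test again. A woman who conceives shortly before or after the screening test could start study drug, or continue it to week 24, unless the pregnancy comes to light at a general review. What is at stake is participant safety under a criterion the protocol itself sets. The trial's inference is not affected.

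**Working it through.** The plan states no figure to reproduce here. The check is a count of listed assessments, followed by simple arithmetic on the schedule.

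**Step 1: visits.** First dose follows baseline. Follow-up at weeks 2 and 4 and then every 4 weeks gives weeks 2, 4, 8, 12, 16, 20 and 24, taking week 24 as the end. The basis for that is the last blood draw and MRI in the protocol and the 24-week weight change in the SAP. This makes 1 + 7 = 8 occasions after screening.

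**Step 2: what is listed at each.**

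| Occasion | Listed assessments | Pregnancy test listed |
|---|---|---|
| Screening | ICD-10 diagnosis, history, examination, urine drug screen, EKG, urine pregnancy test | 1 |
| Baseline / first dose | body measurements, fasting bloods, breath CO, craving scale, cigarette count, PANSS, side effects questionnaire; MRI on another day for imaging subjects | 0 |
| Weeks 2, 4, 8, 12, 16, 20, 24 | weight, breath CO, side effects; waist, scales and symptoms every 4 weeks; bloods at 12 and 24; MRI at 24 | 0 |

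The blood panel names its analytes one by one, and hCG is not among them. The total is 1 listed test at screening and 0 on the 8 later occasions.

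**Step 3: dosing time after the only listed test.** 24 weeks × 7 = 168 days, all of it after the screening test. To this is added the screening-to-dose interval, whose length the documents do not give. For the imaging subjects, 30/60 = 50% of the sample, that interval also has to accommodate an MRI on a separate day.

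**Step 4: effect of adding tests.** The longest stretch of dosing between listed tests would be:

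- test at first dose only: 24 × 7 = 168 days, but entry status is checked on the day it matters;
- first dose, week 12 and week 24: 12 × 7 = 84 days;
- first dose and weeks 4, 8, 12, 16, 20 and 24: 4 × 7 = 28 days.

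The last option uses 1 + 6 = 7 tests per woman of childbearing potential. If all 60 subjects were such women, the ceiling is 7 × 60 = 420 tests.

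**Step 5: what cannot be computed.** Expected pregnancies would need the number of women of childbearing potential and a conception rate. The documents give neither, so no such figure is offered.

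**The case against.** The strongest reply is that the protocol is short and plainly does not write down every test it relies on. Exclusion 5 turns on TSH and T4, yet no thyroid test appears at any visit. Exclusion 4 turns on transaminases, yet the screening visit lists no blood test. The baseline list is introduced as inclusive and need not be complete. A reader might infer from the silence that the sponsor planned no further pregnancy tests; the documents do not support that. They show only that none is listed. This part of the reply stands and limits the claim.

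Second, the screening test does implement the entry criterion, the interval to first dose may be short, and an investigator reviews medical status at the visits. All of this is fair. But the interval is not bounded in the text, and a general review is not a test and could miss an early pregnancy.

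Third, the counts of visits and days describe the schedule and do not measure harm. With 1:1 randomization, half the subjects receive placebo, and the documents say nothing on fetal risk from either drug. This also stands: the counts show where tests are absent and imply no expected number of affected pregnancies.

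Fourth, testing every 4 weeks is a choice. Nothing in the documents fixes an interval; weeks 12 and 24, when blood is already drawn, would be another option. That is right, and it is why the first-dose test is treated as the core change and the later frequency as a matter of judgement.

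One might also read in a lack of contraception or pregnancy-handling rules. The public text shows none, but it is too brief for that to prove anything, and this point does not rest on it.

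**Conclusion.** The point holds as a gap in the listed schedule: one pregnancy test at screening, and 0 on the 8 occasions from first dose to week 24, with 168 planned dosing days after the only test named. The firmest part is the day of first dose. Baseline is a separate, later visit, no maximum interval is set, and no listed test confirms the pregnancy exclusion when drug is handed over. The on-treatment part also holds, though less tightly, because some clinical detection at visits is possible.

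This assumes that the listed schedule is what sites follow, that dosing ends at week 24, and that some women of childbearing potential enrol, as the protocol's own test anticipates. It is a low-cost safety improvement. Sample size, power and the planned analysis are unaffected.

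**What to change.** For women of childbearing potential, write into the protocol:

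1. **Core change:** repeat the same urine test on the day of first dose, before drug is handed over.
2. **During treatment:** repeat it at existing dispensing visits, before drug is handed over. Weeks 4, 8, 12, 16 and 20 are a reasonable choice. Week 2 is left out because it falls between the first-dose and week 4 tests; it could be added if the sponsor wants a check before the dose is doubled.
3. **Closing test** at week 24.
4. **On a positive result:** withhold study drug and keep the subject in the intent-to-treat analysis the SAP already specifies.

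If repeat tests are already done in practice, the change is only to list them.

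**Cost:** protocol wording and up to 7 dipsticks per woman concerned, with a ceiling of 420 in the extreme case worked above. The core change alone is 1 per woman, at most 60. No visit is added. The downsides are a urine sample and a few minutes at each of those visits, and a false positive would hold drug until resolved.

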Naltrexone and Bupropion Combination on Obese, Smoking
Patients With Schizophrenia

NCT02736474

2015.12.30.

The sample of 60 evaluable subjects will have 80% power to detect a 4.5 kg differential change in weight between treatment groups, which is seen as a clinically meaningful weight change over 24 weeks, and 6 kg as the estimate of standard deviation for NB treatment based on previously published data of NB in overweight and obese but otherwise healthy people over 6 months. Although the Apovian et al. study was 56 weeks in duration, the study had a midpoint analysis at 28 weeks which showed that almost all of the weight loss had already occurred, making this data useful for our power analysis. To achieve power=0.80, with a two-tailed significance level of 0.05, 30 subjects per treatment group will be required.

All analyses will be performed on an intent-to-treat basis. Analyses will be carried using a mixed model repeated-measures analysis of variance with fixed effects of visit, treatment group, baseline score, and visit x treatment and visit x baseline score interactions and random participant-specific intercepts and slopes. Potential confounding variables will be included as covariates. The effect of treatment on 24-week change from baseline will be determined by the estimated regression coefficient of the visit x group interaction term. Differences between the treatment groups on categorical variables will be analyzed using the Fisher exact test or Chi-square

test. Independent sample t tests will be used to compare group differences on continuous variables.

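### Randomisation is stratified by imaging participation, but the SAP model names neither that stratum nor its interaction with visit, so the treatment standard error is too large if the strata change weight differently

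*Protocol*

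**What the plan says.** The Protocol's Subjects paragraph sets the two strata: "A total number of 60 subjects will be recruited for the study with 30 of them to complete the imaging assessment". That leaves 30 subjects outside imaging. Its Baseline visit paragraph describes 1:1 allocation by "permuted block randomization, stratified by imaging assessment participation".

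The SAP's analysis paragraph specifies a mixed model with "fixed effects of visit, treatment group, baseline score, and visit x treatment and visit x baseline score interactions and random participant-specific intercepts and slopes". The treatment test is tied to one term: "The effect of treatment on 24-week change from baseline will be determined by the estimated regression coefficient of the visit x group interaction term". The only other route into the model is the sentence "Potential confounding variables will be included as covariates", which names no variable. Neither document says how the 30 imaging subjects are chosen or whether they are expected to lose weight differently.

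**The concern.** A factor used to restrict the randomisation normally belongs in the analysis. Blocking within imaging and non-imaging subjects balances the arms in each stratum, so any difference between strata cancels from the treatment contrast. If the model omits the stratum, that difference stays in its variance estimate. The reported standard error is then larger than the true one, the confidence interval is too wide, and the test rejects less often than 5% under the null.

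Here the treatment effect is a difference in change over visits. What matters is therefore whether the strata differ in change, not in level. The term needed is stratum × visit, and nothing in the SAP provides for it. At stake is precision in a 60-subject trial whose planned power is only a little above 80%.

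**Working it through.** **Inputs.** From the SAP's power paragraph: difference 4.5 kg, SD 6 kg, two-sided 0.05, power 80%, 30 per group. From the Protocol: 1:1 allocation and strata of 30 and 30, hence 15 per arm in each stratum. Assumed, because the documents do not give it: the stratum difference *d* in mean 24-week weight change.

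**Step 1: the plan's own figure.** n per group = 2 × (1.96 + 0.842)² × 6² / 4.5² = 27.9, so 28 by the normal approximation; the noncentral t gives 29. Power at 30 per group is 81.5% (t) or 82.8% (normal). The stated 30 is reproduced.

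**Step 2: a single 24-week endpoint.** Two equal strata differing by *d* add *d*²/4 to the variance within an arm. With within-stratum SD *s*:

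- true SE = *s* × √(2/30)
- SE reported without the stratum ≈ √(*s*² + *d*²/4) × √(2/30)
- ratio = √(1 + *d*²/(4*s*²))

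The SAP does not say whether 6 kg includes variation between strata, so both readings are shown.

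*Reading A: 6 kg is the total SD.* Then *s*² = 36 − *d*²/4, and the reported SE is 6 × √(2/30) = 1.549 kg. Type I error and power come from 40,000 simulated trials per setting, analysed with and without the stratum.

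| *d* (kg) | True SE (kg) | SE excess | Type I error without stratum | Power without / with stratum |
|---|---|---|---|---|
| 2 | 1.528 | 1.4% | 4.7% | 81.7% / 82.4% |
| 3 | 1.500 | 3.3% | 4.2% | 81.9% / 83.5% |
| 4.5 | 1.436 | 7.9% | 3.3% | 83.2% / 86.9% |

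The normal approximation gives the same picture about one point higher. With r = (*d*²/4)/36 and 4.5/1.549 = 2.905, power is Φ((2.905 − 1.96)/√(1 − r)) without the stratum and Φ(2.905/√(1 − r) − 1.96) with it. The results are 83.1% / 83.8%, 83.5% / 85.1% and 84.6% / 88.0%.

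*Reading B: 6 kg is the within-stratum SD.* The ratio is √(1 + *d*²/144) = 1.014, 1.031 and 1.068. Without the stratum the residual sum of squares absorbs 60 × *d*²/4 over 58 degrees of freedom, which refines the ratio to √(1 + (60/58) × *d*²/144) = 1.014, 1.032 and 1.070. The simulated values below come from 200,000 trials per setting.

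| *d* (kg) | SE excess | Type I error without stratum | Power without / with stratum |
|---|---|---|---|
| 0 | none | – | 81.5% / 81.5% |
| 2 | 1.4% | 4.7% | 80.7% / 81.4% |
| 3 | 3.2% | 4.3% | 79.8% / 81.5% |
| 4.5 | 7.1% | 3.6% | 77.6% / 81.6% |

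The mean estimate was 4.49 to 4.50 kg throughout, so there is no bias.

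**Step 3: a model of the SAP's type.** The setting is 60 subjects, visits at weeks 2, 4, 8, 12, 16, 20 and 24, visit as linear time, random intercepts and slopes, and REML. Variance components are assumed:

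- Set 1: intercept SD 1.5, slope SD 5.4 per 24 weeks, residual SD 2; 70 trials.
- Set 2: intercept SD 1, residual SD 1, slope variance including the stratum part held at 35; 60 trials.

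Mean SE of visit × group:

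| Setting | SAP terms | + stratum | + stratum and stratum × visit |
|---|---|---|---|
| Set 1, *d* = 4.5, complete data | 1.660 | 1.660 | 1.552 |
| Set 1, *d* = 4.5, 20% dropout | 1.743 | 1.745 | 1.616 |
| Set 2, *d* = 0 | 1.592 | 1.592 | 1.595 |
| Set 2, *d* = 3 | 1.591 | 1.591 | 1.545 |
| Set 2, *d* = 6 | 1.592 | 1.592 | 1.384 |

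In Set 1 the excess is 1.660/1.552 = 1.070 with complete data and 1.743/1.616 = 1.079 with dropout. In Set 2 at *d* = 6 the estimates had an empirical SD of 1.423, well below the SE of 1.592 from the SAP terms.

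The main effect does nothing useful because, with complete data on a common schedule, the visit × group estimate is a group contrast of per-subject slopes, and a stratum main effect enters only the intercept. A further check on per-subject slopes (6,000 trials) gave SE ratios of 1.015, 1.033 and 1.072 at *d* = 2, 3 and 4.5.

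**The case against.** The strongest reply is that the harm depends on a quantity found nowhere in the documents. Nothing says that imaging participation predicts weight change, and the 7 to 8% excess needs a gap between strata as large as the treatment effect the trial is powered for. This stands, and it is why the size is given as a range starting at zero.

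Second, the SAP's 6 kg comes from published data with no mention of strata, so it reads most naturally as a total SD. Power without the stratum then stays above 80% at every difference examined. This also stands: the fall to 77.6% belongs to Reading B only.

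Third, the SAP already adjusts for baseline score and its interaction with visit. A stratum difference that acts through baseline weight is absorbed there, so *d* should be read as what remains after that adjustment. This is correct.

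Fourth, the error is conservative, so validity is not threatened. Agreed.

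Fifth, the mixed-model runs are small and rest on assumed variance components. Their SEs are usable and agree with the closed form; their rejection rates are not relied on.

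The argument that the sentence on confounders already covers the stratum does not stand. It names no variable, and a covariate entered as a main effect leaves the tested coefficient's SE essentially where it was.

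**Conclusion.** The concern holds. The design uses a stratum that the analysis model does not name, and the one term that would recover the precision, stratum × visit, is not provided for. If the strata change weight differently after adjustment for baseline, the SE of the treatment effect is overstated: slightly at 2 to 3 kg, and by 7 to 8% at 4.5 kg. If they do not differ, omission costs nothing and adjustment costs almost nothing.

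This is a modest, conditional loss of efficiency, with type I error below its nominal level and no bias. Under the total-SD reading it is a forgone gain, not a failure to reach 80% power. The figures assume exact 15/15 balance in each stratum and, in the mixed model, visit as a linear trend. The change is worth making because the stratum is fixed before allocation, already recorded, and part of the design.

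**What to change.** In the between-group mixed models fitted to all 60 subjects, add imaging participation and its interaction with visit, matching the treatment the SAP already gives to baseline score. One sentence in the SAP is enough:

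> The model will also include imaging participation (yes/no), as recorded for randomisation, and imaging participation × visit as fixed effects.

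The terms should not be added for the MRI outcomes, where every subject is in the same stratum.

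The cost is two model terms: one degree of freedom each if visit is a linear slope, or one per visit contrast for the interaction if visit is categorical. No new data are needed.

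As a separate matter of wording, which carries no weight in this conclusion, the sentence on confounders could be limited to baseline variables named before unblinding, with any other adjustment labelled a sensitivity analysis.

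### Is the past-week cigarette count lost after baseline because no follow-up visit names it?

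*Protocol*

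**What the plan says.** Smoking amount is asked twice before treatment. At screening the history is taken "including current medications, substance use and number of cigarettes smoked daily"; at baseline, item 5 is "number of cigarettes smoked in the past week". Baseline also has breath CO (item 3) and a craving Visual Analogue Scale (item 4).

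The Protocol's Follow-up visits paragraph gives an every-visit list: "Weight, breath CO, and possible side effects will be assessed during each visit". A second, four-weekly list opens "Waist circumference, scales, the clinical" and runs on to the symptoms assessment. Bloods follow at weeks 12 and 24, and MRI at week 24 for the imaging subset. Neither list names the cigarette count.

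The SAP describes one model, "with fixed effects of visit, treatment group, baseline score, and visit x treatment and visit x baseline score interactions", with random participant intercepts and slopes. It names one outcome, weight, in the power statement.

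**The concern.** Quitting is part of the reason subjects enrol: the inclusion criteria ask for a "desire to lose weight and quit smoking". A count taken at baseline and never again has nothing to be compared with, and the SAP's model needs visit values to set against a baseline score. If the count is not asked at follow-up, change in self-reported smoking cannot be worked out later, because answers not taken at the visit are gone. One breath reading per visit does not say how many cigarettes were smoked in the week before.

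A side point looks similar. The exclusions include "clinically significant TSH and/or T4 abnormalities" and a transaminase limit, yet no screening or baseline list names a thyroid test, and liver enzymes would come at best from the baseline metabolic profile, drawn once subjects are already called eligible.

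**Working it through.** **Is any stated figure affected?** The only design figure is the sample size for weight. Inputs from the SAP: difference 4.5 kg, SD 6 kg, two-sided 0.05, power 0.80.

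n per group = 2 × (1.960 + 0.842)² × 6² / 4.5² = 2 × 7.85 × 36 / 20.25 = 27.9, so 28. The t-test version gives 28.9, so 29. The SAP states 30, at which power is 0.828 (normal) or 0.815 (t test). The figure reproduces, and nothing in it uses a cigarette count.

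**Visits.** Weeks 2, 4, 8, 12, 16, 20 and 24 make 7. The four-weekly list applies at weeks 4, 8, 12, 16, 20 and 24, which makes 6.

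**Baseline items set against follow-up.**

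| Baseline item | Where it reappears |
|---|---|
| 1. Height, weight, waist | Weight every visit; waist four-weekly; height not repeated |
| 2. Bloods | Weeks 12 and 24 |
| 3. Breath CO | Every visit |
| 4. Craving Visual Analogue Scale | Not named; *scales* is the only candidate |
| 5. Past-week cigarettes | Not named; *scales* is the only candidate |
| 6. PANSS | Symptoms assessment, or *scales* |
| 7. Side effects | Every visit |

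The four-weekly items are described as repeated, which points back to the baseline list. If PANSS is the symptoms assessment, only items 4 and 5 are left for *scales*, and a single craving scale fits the plural poorly. Against that, a count is not literally a scale, and PANSS may be one of the scales. The text does not settle it.

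**Size under each reading (60 subjects, 60 × 7 = 420 visit records).**

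- *Scales* includes the count: 60 × 6 = 360 of 420, week 24 included. The SAP's 24-week change can be computed. Week 2 is absent, as it is for waist and symptoms.
- *Scales* excludes the count: 0 of 420.
- Breath CO on either reading: 420 of 420.

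**Declared analyses that need the count.** None. The baseline score in the SAP model is a generic term for whichever outcome is being modelled. It does not promise a follow-up value for every baseline item, and height shows that some items are taken once.

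**Side point.** The baseline blood sample has 11 items and TSH/T4 is in 0 of them. The Intervention paragraph, however, lets treatment start only after screening and once the criteria have been confirmed. A thyroid exclusion cannot be confirmed without thyroid information, so the test is implied though unnamed. The metabolic profile is drawn before study drug is given.

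**The case for a change.** The strongest case for a change is that the follow-up paragraph is itemised with care. It lists all 11 blood items again and names breath CO again, so leaving out the count reads as an omission. The baseline items actually called scales are the craving measure and PANSS, and on ordinary wording the count falls outside. Smoking is in the trial's title and its eligibility criteria. One extra question per visit costs almost nothing, and a missed answer cannot be recovered.

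Much of this stands. The count is not named after baseline, *scales* is undefined, and on the narrow reading self-reported change is lost. Three things limit its force. First, this shows ambiguity and not absence, since the wider reading is reasonable and gives six post-baseline values. Second, the loss on the narrow reading falls on an outcome that the SAP does not declare. Smoking is still followed by an objective measure at every visit, and the baseline count can still describe the groups or serve as a covariate. Third, asking for a week 2 count is a preference, because a four-weekly schedule is an ordinary choice.

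Power for a change in the count could be calculated, but it would describe an endpoint the plan does not have and would not measure any loss caused by the wording.

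**Conclusion.** The observation is accurate, but it is missing detail and not an error. Depending on one undefined word, between 0 and 360 of 420 post-baseline cigarette counts are planned. No stated analysis, sample size or decision rule changes anywhere in that range, and breath CO is complete by design. A study team settles the meaning of *scales* when it builds the case report form. The thyroid and transaminase point is likewise a matter of unnamed tests under a requirement that is already written down.

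This rests on two assumptions: that the count is not a declared outcome, which is how the SAP reads, and that the stated confirmation of criteria before treatment is carried out. If change in self-reported cigarettes were made an outcome, the narrow reading would leave it without data and the point would have to be reopened.
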